6.3 Subject numbering, treatment assignment, randomization

6.3.1 Subject numbering

Each subject is identified in the study by a Subject Number (Subject No.) that is assigned when the subject is first enrolled for screening and is retained as the primary identifier for the subject throughout his/her entire participation in the trial. The Subject No. consists of the Center Number (Center No.) (as assigned by Novartis to the investigative site) with a sequential subject number suffixed to it, so that each subject is numbered uniquely across the entire database. Once assigned to a subject, the Subject No. will not be reused. Upon signing the informed consent form, the subject is assigned to the next sequential Subject No. available.

6.3.2 Treatment assignment, randomization

At BSL visit, all eligible subjects will be randomized via Interactive Response Technology (IRT) to one of the treatment arms. The investigator or his/her delegate will contact the IRT after confirming that the subject fulfills all the inclusion/exclusion criteria. The IRT will assign a randomization number to the subject, which will be used to link the subject to a treatment arm and will specify a unique medication number for the first package of study treatment to be dispensed to the subject. The randomization number will not be communicated to any of the site staff.

Starting at Week 16, subjects who have been randomized to placebo at baseline will receive secukinumab 3 mg/kg i.v. up to Week 48. Although the investigator, site personnel and subjects are unblinded to current treatment assignment after Week 16 (as all subjects will be on secukinumab 3 mg/kg i.v starting at Week 16), original treatment assignment, as per baseline randomization, will remain blinded to the subject, investigator, and site personnel until after final database lock and analyses.

All efficacy and safety assessments should be done prior to calling IRT.

The randomization numbers will be generated using the following procedure to ensure that treatment assignment is unbiased and concealed from subjects and investigator staff. A subject randomization list will be produced by the IRT provider using a validated system that automates the random assignment of subject numbers to randomization numbers. These randomization numbers are linked to the different treatment arms, which in turn are linked to medication

numbers. A separate medication list will be produced by or under the responsibility of Novartis Global Clinical Supply (GCS) using a validated system that automates the random assignment of medication numbers to packs containing the study treatment.

The subjects will be stratified at randomization according to disease condition (i.e. AS or nr-axSpA). Not more than 20% of randomized subjects will be TNF-IR to ensure a representative subject population for the assessment of efficacy and safety.

The randomization scheme for subjects will be reviewed and approved by a member of the Randomization Office.

6.4 Treatment blinding

This is a double-blind, randomized treatment trial.

Subjects, investigators, investigator staff and persons performing the assessments, will remain blind to the identity of the treatment from the time of randomization until database lock, using the following methods: (1) Randomization data are kept strictly confidential until the time of unblinding and will not be accessible by anyone else involved in the study with the exception of the bioanalyst, (2) the identity of the treatments will be concealed by the use of study treatment in form of vials, filled with secukinumab or placebo that are identical in appearance.

The bioanalyst will have access to the randomization list to facilitate analysis of the PK [REDACTED] (i.e. to avoid the unnecessary analysis of placebo samples). Whenever needed or requested by the clinical team, the bioanalyst will share information from PK measurements before clinical database lock in a blinded fashion with the pharmacokineticist.

Starting at Week 16, subjects who have been randomized to placebo at baseline will start receiving secukinumab 3 mg/kg i.v. every four weeks up to Week 48. Although subjects, investigators, investigator staff and persons performing the assessments are unblinded to current treatment assignment after Week 16 (as all patients will be on secukinumab 3 mg/kg i.v. at Week 16), original treatment assignment, as per baseline randomization, will remain blinded to subjects, investigator staff and persons performing the assessments until after final database lock and analyses.

Unblinding will occur in the case of subject emergencies (see [Section 6.6.3](#)) and at the conclusion of the study.

Unblinding of the Global core CTT members will also occur at the time of the primary analysis database lock (see [Section 12.7](#)).

The hsCRP results from samples collected during the treatment period will be revealed to sites only after the database lock and analyses are completed. The hsCRP results from samples collected during the treatment period 1 will be revealed to Global core CTT members at the time of the primary interim analysis database lock.

6.5 Dose escalation and dose modification

Dose modifications of the investigational study drug are not permitted.

6.5.1 Dose escalation guidelines

With the proposed i.v. regimen anticipated to provide exposures of secukinumab similar to the C_{avg} and C_{max} achieved with 300 mg s.c. and C_{trough} consistently above those achieved by 150 mg s.c., dose escalations will not be provisioned for in this study.

6.5.1.1 Starting dose

The starting dose at BSL for the active arm in the study will be secukinumab 6 mg/kg. The placebo group will receive as starting dose at BSL an appropriate infusion volume matching secukinumab 6 mg/kg.

6.5.2 Dose modifications

Study treatment interruptions are not permitted with the following exceptions:

- If, in the opinion of the investigator, a subject is deemed to be placed at a significant safety risk unless dosing is temporarily interrupted. In such cases study treatment should be interrupted only during the time that this risk is present and ongoing. Study treatment can be restarted at the next scheduled visit after resolution of the safety risk.
- If any prohibited medication described in [Table 6-1](#) requires the interruption of the study treatment.

Study treatment interruptions must be recorded on the corresponding Dosage Administration Record eCRF page and all assessments should be completed as scheduled.

6.5.3 Follow-up for toxicities

Subjects whose treatment is interrupted or permanently discontinued due to an adverse event or clinically significant abnormal laboratory value, must be followed up in accordance with what is clinically indicated per the investigator until resolution or stabilization of the event, whichever comes first. Appropriate clinical experts such as ophthalmologist, endocrinologist, dermatologist, psychiatrist, etc., should be consulted as deemed necessary.

6.5.3.1 Follow up on potential drug-induced liver injury (DILI) cases

An increase in transaminase increase combined with total bilirubin (TBIL) increase may be indicative of potential DILI and should be considered as clinically important events.

The threshold for potential DILI may depend on the subject's baseline AST/ALT and TBIL value; subjects meeting any of the following criteria will require further follow-up as outlined below:

- For subjects with normal ALT and AST and TBIL value at baseline: AST or ALT > 3.0 x ULN combined with TBIL > 2.0 x ULN
- For subjects with elevated AST or ALT or TBIL value at baseline: [AST or ALT > 2 x baseline AND > 3.0 x ULN] OR [AST or ALT > 8.0 x ULN], combined with [TBIL > 2 x baseline AND > 2.0 x ULN]

Medical review needs to ensure that liver test elevations are not caused by cholestasis, defined as ALP elevation > 2.0 x ULN with R value < 2 in subjects without bone metastasis, or elevation of ALP liver fraction in subjects with bone metastasis.

Note: The R value is calculated by dividing the ALT by the ALP, using multiples of the ULN for both values. It denotes whether the relative pattern of ALT and/or ALP elevation is due to cholestatic ($R \leq 2$), hepatocellular ($R \geq 5$), or mixed ($R > 2$ and < 5) liver injury.

In the absence of cholestasis, these subjects should be immediately discontinued from study treatment, and repeat LFT testing as soon as possible, preferably within 48 hours from the awareness of the abnormal results. The evaluation should include laboratory tests, detailed history, physical assessment, and the possibility of liver metastasis or new liver lesions, obstructions/compressions, etc.

1. Laboratory tests should include ALT, AST, albumin, creatine kinase, TBIL, direct and indirect bilirubin, GGT, prothrombin time (PT)/INR, and alkaline phosphatase.
2. A detailed history, including relevant information, such as review of ethanol, concomitant medications, herbal remedies, supplement consumption, and history of any pre-existing liver conditions or risk factors, should be collected.
3. Further testing for acute hepatitis A, B, C or E infection and liver imaging (e.g. biliary tract) may be warranted.
4. Obtain PK sample as close as possible to last dose of secukinumab.
5. Additional testing for other hepatotropic viral infection (CMV, EBV or HSV), autoimmune hepatitis or liver biopsy may be considered as clinically indicated or after consultation with specialist/hepatologist.

All cases confirmed on repeat testing meeting the laboratory criteria defined above, with no other alternative cause for LFT abnormalities identified, should be considered as “medically significant,” and thus, meet the definition of SAE and should reported as SAE using the term “potential drug-induced liver injury.” All events should be followed up with the outcome clearly documented.

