16.6 Appendix 6: Liver event and laboratory trigger definitions and follow-up requirements

Table 16-3 Liver Events and Laboratory Trigger Definitions

	Definition/ threshold
LIVER LABORATORY TRIGGERS	$3 \times \text{ULN} < \text{ALT} / \text{AST} \leq 5 \times \text{ULN}$ $1.5 \times \text{ULN} < \text{TBL} \leq 2 \times \text{ULN}$
LIVER EVENTS	ALT or AST $> 5 \times \text{ULN}$ ALP $> 2 \times \text{ULN}$ (in the absence of known bone pathology) TBL $> 2 \times \text{ULN}$ (in the absence of known Gilbert syndrome) ALT or AST $> 3 \times \text{ULN}$ and INR > 1.5

Potential Hy's Law cases (defined as ALT or AST > 3 × ULN and TBL > 2 × ULN [mainly conjugated fraction] without notable increase in ALP to > 2 × ULN)
Any clinical event of jaundice (or equivalent term)
ALT or AST > 3 × ULN accompanied by (general) malaise, fatigue, abdominal pain, nausea, or vomiting, or rash with eosinophilia
Any adverse event potentially indicative of a liver toxicity *

* These events cover the following: hepatic failure, fibrosis and cirrhosis, and other liver damage-related conditions; non-infectious hepatitis; benign, malignant and unspecified liver neoplasms
TBL: total bilirubin; ULN: upper limit of normal

Table 16-4 Follow up Requirements for Liver Events and Laboratory Triggers

Criteria	Actions required	Follow-up monitoring
Potential Hy's Law case ^a	Discontinue the study drug immediately Hospitalize, if clinically appropriate Establish causality Complete appropriate eCRF pages	ALT, AST, TBL, Alb, PT/INR, ALP and γGT until resolution ^c (frequency at investigator discretion)
ALT or AST > 8 × ULN	Discontinue the study drug immediately Hospitalize if clinically appropriate Establish causality Complete appropriate eCRF pages	ALT, AST, TBL, Alb, PT/INR, ALP and γGT until resolution ^c (frequency at investigator discretion)
> 3 × ULN and INR > 1.5	Discontinue the study drug immediately Hospitalize, if clinically appropriate Establish causality Complete appropriate eCRF pages	ALT, AST, TBL, Alb, PT/INR, ALP and γGT until resolution ^c (frequency at investigator discretion)
> 5 to ≤ 8 × ULN	Repeat LFT within 48 hours If elevation persists, continue follow-up monitoring If elevation persists for more than 2 weeks , discontinue the study drug Establish causality Complete appropriate eCRF pages	ALT, AST, TBL, Alb, PT/INR, ALP and γGT until resolution ^c (frequency at investigator discretion)

Criteria	Actions required	Follow-up monitoring

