> 3 × ULN accompanied by symptoms ^b	Discontinue the study drug immediately Hospitalize if clinically appropriate Establish causality Complete appropriate eCRF pages	ALT, AST, TBL, Alb, PT/INR, ALP and γGT until resolution ^c (frequency at investigator discretion)
> 3 to ≤ 5 × ULN (patient is asymptomatic)	Repeat LFT within the next week If elevation is confirmed, initiate close observation of the patient	Investigator discretion Monitor LFT within 1 to 4 weeks
ALP (isolated)		
> 2 × ULN (in the absence of known bone pathology)	Repeat LFT within 48 hours If elevation persists, establish causality Complete appropriate eCRF pages	Investigator discretion Monitor LFT within 1 to 4 weeks or at next visit
TBL (isolated)		
> 2 × ULN (in the absence of known Gilbert syndrome)	Repeat LFT within 48 hours If elevation persists, discontinue the study drug immediately Hospitalize if clinically appropriate Establish causality Complete appropriate eCRF pages	ALT, AST, TBL, Alb, PT/INR, ALP and γGT until resolution ^c (frequency at investigator discretion) Test for hemolysis (e.g., reticulocytes, haptoglobin, unconjugated [indirect] bilirubin)
> 1.5 to ≤ 2 × ULN (patient is asymptomatic)	Repeat LFT within the next week If elevation is confirmed, initiate close observation of the patient	Investigator discretion Monitor LFT within 1 to 4 weeks or at next visit
Jaundice	Discontinue the study drug immediately Hospitalize the patient Establish causality Complete appropriate eCRF pages	ALT, AST, TBL, Alb, PT/INR, ALP and γGT until resolution ^c (frequency at investigator discretion)
Any AE potentially indicative of a liver toxicity*	Consider study drug interruption or discontinuation Hospitalization if clinically appropriate Establish causality Complete appropriate eCRF pages	Investigator discretion

* These events cover the following: hepatic failure, fibrosis and cirrhosis, and other liver damage-related conditions; non-infectious hepatitis; benign, malignant and unspecified liver neoplasms

Criteria	Actions required	Follow-up monitoring
-----------------	-------------------------	-----------------------------

TBL: total bilirubin; ULN: upper limit of normal

^a Elevated ALT/AST > 3 × ULN and TBL > 2 × ULN but without notable increase in ALP to > 2 × ULN

^b (General) malaise, fatigue, abdominal pain, nausea, or vomiting, or rash with eosinophilia

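### Protocol 6.5.3.1 requires an immediate stop for a narrow band of mixed-pattern liver injury; the ALT/AST rows of Table 16-4 give a later stop or none, and the liver-event pathway does not point to 6.5.3.1 (minor)

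*Protocol*

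**What the plan says.** **Section 6.5.3.1.** For normal baseline tests, potential DILI is AST or ALT above 3×ULN with total bilirubin (TBL) above 2×ULN. Medical review must rule out "cholestasis, defined as ALP elevation > 2.0 x ULN with R value < 2" (the rule for subjects without bone metastasis). R is ALT divided by ALP, each in ×ULN. For the remaining cases: "In the absence of cholestasis, these subjects should be immediately discontinued from study treatment". A repeat test, a work-up with a PK sample and, for confirmed cases with no other cause, an SAE report follow.

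**Appendix 6 (16.6).** In Tables 16-3 and 16-4 a potential Hy's Law case, which stops at once, is ALT or AST above 3×ULN with TBL above 2×ULN "but without notable increase in ALP to > 2 × ULN" (note a of Table 16-4). R plays no part. Table 16-4 also stops at once for:
- ALT or AST above 8×ULN;
- a value above 3×ULN with INR above 1.5 or a listed symptom;
- jaundice.

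Otherwise:
- Above 5 to 8×ULN: repeat within 48 hours, and stop if the elevation lasts more than two weeks.
- Above 3 to 5×ULN without symptoms: repeat within a week and observe if confirmed; the follow-up column says "Monitor LFT within 1 to 4 weeks".
- Isolated TBL above 2×ULN: repeat within 48 hours, then "If elevation persists, discontinue the study drug immediately".

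**Section 10.2.1** directs the site to Section 16.6 for definitions and actions, and to 9.1.1 for discontinuation. It cites Tables 16-1 and 16-2, but the liver tables are 16-3 and 16-4. **Section 9.1.1** does not list the 6.5.3.1 criteria. Its laboratory item rests on the investigator's judgment.

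**The concern.** The two parts of the protocol separate obstructive from hepatocellular injury by different tests. Section 6.5.3.1 needs both a raised ALP and a low R before it exempts a case. Appendix 6 uses the ALP cutoff alone. A mixed pattern, with ALP above 2×ULN but ALT more than twice as high in ×ULN terms, therefore has a mandatory stop in one place and a slower action in the other. A site handling a liver event would naturally open 10.2.1 and then the table of required actions, and nothing on that route names 6.5.3.1.

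At stake are how soon study drug stops in a subject with possible drug-induced liver injury, and whether the 6.5.3.1 work-up and SAE assessment are started.

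**Working it through.** The plan gives no figure for this point, so the check sets the two rules side by side. Values are in ×ULN. Assumed throughout: normal baseline, AST ≤ 8, no listed symptom, no jaundice, INR ≤ 1.5.

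**Where the rules differ**
1. Section 6.5.3.1 stops at once if ALT or AST > 3 and TBL > 2, unless ALP > 2 and R < 2.
2. Table 16-4 stops at once if ALT or AST > 3, TBL > 2 and ALP is not > 2, or if ALT or AST > 8.
3. A case caught by step 1 but not step 2 must have ALP > 2, R not below 2, and ALT and AST ≤ 8.
4. ALT = R × ALP, so ALP > 2 with R ≥ 2 gives ALT > 4. ALT ≤ 8 with ALP > 2 gives R < 4.
5. The ALP band at a given ALT runs from above 2 up to ALT/2: 2.25 at ALT 4.5, 2.5 at ALT 5, 3 at ALT 6, 4 at ALT 8.

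At exactly R = 2 section 6.5.3.1 is itself ambiguous: its definition of cholestasis uses R < 2, while its Note calls R ≤ 2 cholestatic. The clear band is R > 2.

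**Examples, all with TBL 2.5 and AST no higher than ALT**

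| ALT | ALP | R | 6.5.3.1 | Table 16-4, Hy's Law and ALT/AST rows |
|---|---|---|---|---|
| 4.5 | 2.1 | 4.5/2.1 = 2.14 | stop now | repeat within a week, observe |
| 5.5 | 2.2 | 5.5/2.2 = 2.50 | stop now | repeat in 48 hours, stop after more than 2 weeks |
| 4.5 | 1.9 | 4.5/1.9 = 2.37 | stop now | stop now (potential Hy's Law) |
| 4.5 | 2.5 | 4.5/2.5 = 1.80 | exempt as cholestasis | repeat within a week, observe |

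Only the first two rows differ on the immediate stop. If a site applied the isolated-TBL row to them, although the bilirubin is not isolated, the result would be a stop after a persistent 48-hour repeat. That is still not an immediate stop.

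Both rules were run over a grid (ALT 3.01 to 12, ALP 0.5 to 6, TBL 2.1, 3 and 5). Every profile stopped at once by 6.5.3.1 but not by Table 16-4 had ALT between 4.01 and 7.96 and R between 2 and 3.98, which matches steps 3 and 4. Switching on jaundice, a listed symptom or INR 1.6 restored the table's immediate stop in each in-band profile tested.

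**Timing, as illustration only.** In the lower part of the band (ALT and AST ≤ 5), suppose the repeat falls on day 7 after awareness and the 1 to 4 weeks run from that repeat. The next test is then on day 14 to 35, against a 28-day infusion interval. The intervals start from different points, since infusions are counted from the visit, and an earlier repeat moves the window forward. SAP Table 5-4 (Group 8) implies post-baseline chemistry at Weeks 4, 8, 12, 16, 24, 32, 40, 52 and 60. Seven of these visits precede a later infusion, and after four of them (Weeks 16, 24, 32, 40) the next infusion visit has no scheduled chemistry. These are analysis windows, and liver follow-up relies on unscheduled repeats, so the count is context and not evidence of harm.

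**The case against.** The strongest reply is that there is nothing to reconcile. Table 16-4 nowhere forbids an earlier stop, and 6.5.3.1 is operative text that states the stop plainly. That stands. A reader might infer that the protocol contradicts itself and that a site cannot comply with both rules; the documents do not support this, because stopping at once satisfies both.

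Other safeguards also count. Cases in the band are liver events under Table 16-3, so 10.2.1 asks for repeat tests, close observation and consideration of interruption. Section 9.1.1 requires a stop for laboratory values the investigator judges a safety risk, and for a serious event not compatible with study drug, which could cover a confirmed 6.5.3.1 case. Appendix 1 asks that action on notable values be discussed with the sponsor. Fatigue is a listed symptom and also BASDAI item 1, so a site that counts disease fatigue would stop some of these subjects anyway. All of this lowers the risk, but each safeguard leaves the decision to judgment, whereas 6.5.3.1 has already made it.

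Finally, the ALP cutoff looks deliberate. The notes to SAP Table 2-3 say that raised ALP may point to obstruction and that such cases may not lead to severe DILI. A reader might infer that the Hy's Law definition is wrong and should be rewritten. It need not be: a narrow Hy's Law category can sit beside the broader R-based stop. Rewriting it would also break its agreement with the Hy's Law row of SAP Table 2-3, which requires ALP below 2×ULN (today the two differ only at exactly 2).

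**Conclusion.** The point holds as a minor patient-safety inconsistency. For the band derived above, 6.5.3.1 requires an immediate stop and the ALT/AST rows of Table 16-4 do not, and the route through 10.2.1, Appendix 6 and 9.1.1 does not lead the site to 6.5.3.1.

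The band is narrow. No frequency is given in the documents and none is estimated here, but such cases should be rare. The result is exact for normal baseline tests only; with raised baseline values 6.5.3.1 adds multiples of baseline.

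A reader might infer that subjects in the band will receive another infusion. The documents do not show that. Above 5×ULN, or if the bilirubin row is used, a persistent elevation would normally stop the drug before the next four-weekly infusion. At ALT above 4 to 5×ULN, with AST also no higher than 5, a further infusion is possible only if 6.5.3.1 goes unread and judgment does not intervene. Nor is there an effect on endpoint definitions, power or the planned analyses.

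**What to change.** - **Table 16-4:** add a row for subjects who meet the 6.5.3.1 potential DILI criteria without cholestasis (that is, not ALP > 2×ULN with R < 2), stating that it includes ALP > 2×ULN with R ≥ 2. Action: discontinue study drug immediately, with work-up and SAE assessment per 6.5.3.1.
- **Potential Hy's Law definition:** leave unchanged in Table 16-3 and note a.
- **9.1.1:** list the 6.5.3.1 criteria and the immediate-stop rows of Table 16-4 as required discontinuations. This also covers ALT > 8×ULN with R < 2, where only the table stops.
- **10.2.1:** refer to 6.5.3.1 and correct the table numbers to 16-3 and 16-4.
- **6.5.3.1:** use one R boundary (< 2) for cholestasis throughout, including the Note.

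The cost is protocol wording and a memo to sites, with no new scheduled tests. No SAP change is needed, because the combined ALT/AST and TBL row of SAP Table 2-3 has no ALP condition and already counts these cases. The downside is a few rare additional early discontinuations; any before Week 16 would count as non-response under the composite variable in Protocol 12.4.2.

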6.6 Additional treatment guidance

6.6.1 Treatment compliance

The investigator should promote compliance by instructing the subject to attend the study visits as scheduled and by stating that compliance is necessary for the subject’s safety and the validity of the study. The subject should be instructed to contact the investigator if he/she is unable for any reason to attend a study visit as scheduled.

Compliance is expected to be 100%, unless temporary interruption is needed for safety reasons as described in [Section 6.5.2](#) or discontinuation of study treatment is required as described in [Section 9.1.1](#). Compliance will also be assessed by a Novartis monitor using information provided by the authorized site personnel.

All dates and times of study treatment administration will be recorded on the appropriate Dosage Administration Record eCRF page.

Pharmacokinetic parameters (measures of treatment exposure) will be determined in all subjects treated with secukinumab, as detailed in pharmacokinetics section (see [Section 8.5.5](#)).

